## Randomization.

The selected patients will be randomized to the: 1) usual care group; 2) audio brochure group; or 3) video brochure group. A random number generator will be used and a 1:2:2 allocation scheme (stratified by gender). We will continue until 160 patients have been randomized (Figure 3).

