**Collection Device.** To assist with the collection of the stool sample, we are also including a dish collection device that makes it easier to collect a stool sample.

**Patient survey** (Appendix I: audio brochure group; Appendix J: video brochure group) and **Medical Record Release (MRR) form** (Appendix K) will be included in the kit with the FIT test. The survey assesses demographic characteristics (e.g. race, education, etc. and telephone number), PMT constructs (e.g. screening barriers), health literacy, perception of access to quality medical care, and satisfaction with educational materials using modified items from an existing satisfaction scale (Likert-type items). Patients will be asked to complete the survey even if they do not complete and return the FIT. Return of the survey will imply consent and participants will receive a \$25 gift card for

Figure 3. Pilot Test Overview and Intervention Components

completing the survey and a \$5 gift card for the return of the signed MRR (Appendix L). Gift cards will be mailed to participants within three business days after receipt of the signed documents. Participants will not have to answer any survey questions they do not want to answer. Participants will be allowed to return the FIT without the survey or MRR. We will call patients who return the survey to decrease missing data, if needed. Based on our previous research, we expect 85% will return the survey and 70% will return a MRR. We will include a stamped addressed return envelope so individuals may return the documents.

**Mailed Reminder (if necessary).** A mailed reminder (Appendix M) will be sent to participants who have not completed the FIT about two weeks after the initial FIT test mailing based on community input. Previous research has shown that FITs are usually returned within a few months. Participants may request a 2nd FIT if they misplaced the first FIT. The study's primary outcome is based on if an individual returns or does not complete the FIT test at two months.

Table 1. Components of Usual Care Group and Intervention Groups			
Component	Group(s)	Description	Theoretical Constructs
Notification Letter	All	• Recommendation for CRC screening	N/A

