Patient Survey	All	• Demographic information • CRC screening history • FIT barriers/facilitators • Satisfaction with materials	• Severity, susceptibility • Rewards, response costs • Self-efficacy, Response-efficacy • Fear/worry
Medical Record Release	All	• Release of CRC screening results	N/A
FIT	Usual Care	• Manufacturing company FIT instructions	N/A
FIT	Audio	• Provides information about CRC screening • Brochure with targeted CRC information for residents of Appalachia, and testimonials • Provides step by step FIT audio instructions	• Severity, susceptibility, response efficacy • Rewards: Concerns and social norms • Fear/worry • Self-efficacy, response efficacy, response costs
FIT	Video	• Provides information about CRC screening • Brochure with targeted CRC information for residents of Appalachia, and testimonials • Provides step by step FIT visual and audio instructions	• Severity, susceptibility, response efficacy • Rewards: Concerns and social norms • Fear/worry • Self-efficacy, response efficacy, response costs
Disposable Gloves	Audio/Video	• Addresses a common patient barrier ("messiness")	• Response Costs
Dish Stool Collection Device	Audio/Video	• Addresses a common patient barrier (ease of collection)	• Response Costs
Screening reminders (if needed)	Audio/Video	• Mailed reminder about the importance of completing CRC screening (FIT)	• Rewards, response costs • Self-efficacy, Response-efficacy

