### **FIT Results and Follow-Up.**

The laboratory will send FIT results to the health center and participants will be notified of results per the health center's regular protocol. Participants with normal FITs will be mailed results including an explanation of the results and the importance of annual FIT completion. Participants with positive FITs will be called by the healthcare system to discuss results and will be referred for colonoscopy using current referral process. Participants with a positive FIT that cannot be reached by multiple attempts by telephone will be sent a letter instructing them to call the clinic for the FIT results. For participants who provide MRR, we will document FIT results. We will also document subsequent referral for colonoscopy, other CRC tests (e.g. colonoscopy) completed, and test results. [name] will assist with issues associated with follow-up of positive FIT that may arise during the study, if needed (all participants). If we do not have a signed MRR, the healthcare system will send us group data by study arm.

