### **Data Analysis.**

The specific aim of this proposal is to conduct a pilot study of the two developed mail-based FIT outreach interventions vs. mailed usual care materials to establish acceptability and obtain preliminary efficacy data on increasing CRC screening. Large sample sizes will not be required to achieve these goals. **Hypothesis A.** Mid-life adults in both intervention groups will have higher satisfaction with materials compared to those in the usual care group (*intervention acceptability*). Linear regression will be used to compare means and estimate differences (intent-to-treat analysis). These acceptability data will be critical to our subsequent application. **Hypothesis B.** FIT return (primary outcome) will be higher among mid-life adults in both intervention groups (audio or video brochures) compared to those in the usual care group (*preliminary efficacy*). We will randomize 64 patients in each intervention arm and 32 patients in the control arm (160 total, stratified for gender in each arm). This sample size will also allow us to characterize proportions +/-6% and means +/-0.13 standard deviation units in each intervention arm. We will estimate FIT return (primary outcome) using proportions for each study group. We assume

a return rate of 20% in control arm, 40% in audio brochure arm (OR=2.7), and 50% in video brochure arm (OR=4.0) based on the literature. Both comparisons (each intervention compared to control) will be a two-sample test of proportions (intent-to-treat analysis) using a one-sided alpha of 0.1 due to the preliminary nature of the study. With these assumptions, we have 96% power for the test of the video intervention and 77% power for the test of the audio intervention. We know that we will not be powered to detect small effect sizes or conduct sophisticated analyses (e.g. gender differences). We will estimate critical parameters with point estimates and 95% confidence intervals and provide a preliminary test of effectiveness on FIT completion. Results will provide preliminary data that will help power the future larger RCT. Data between the healthcare system and the OSU research team will be by secure encrypted email (Appendix O)

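### Randomisation is stratified by gender, but the primary test of FIT return ignores the stratum: a valid plan with a small, cheap improvement available

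*Combined protocol and SAP*

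**What the plan says.** The Randomization section makes gender a stratification factor: "A random number generator will be used and a 1:2:2 allocation scheme (stratified by gender"). The Data Analysis section repeats this with the arm sizes: "We will randomize 64 patients in each intervention arm and 32 patients in the control arm (160 total, stratified for gender in each arm").

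The primary comparison in the same Data Analysis section does not mention gender: "Both comparisons (each intervention compared to control) will be a two-sample test of proportions (intent-to-treat analysis) using a one-sided alpha of 0.1". FIT return is to be estimated by a proportion per study group. No section names a stratified test, a gender covariate or a gender-adjusted estimate.

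Gender appears in the analysis text otherwise only as an example of what the pilot is not powered to do, namely "conduct sophisticated analyses (e.g. gender differences").

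One passage bears on whether the outcome is available by gender. FIT Results and Follow-Up says: "If we do not have a signed MRR, the healthcare system will send us group data by study arm". The protocol expects that some patients will have no signed medical record release (MRR): "Based on our previous research, we expect 85% will return the survey and 70% will return a MRR".

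**The concern.** When a design balances the arms on a factor, the usual practice is to carry that factor into the main analysis. If the factor predicts the outcome, balancing on it removes some chance variation from the difference between arms. An unstratified test still counts that variation in its standard error, so it rejects a true null hypothesis less often than its nominal level and gives up a little power.

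Any loss would matter most for the audio comparison, which has the lower stated power (77%). The pilot's estimates are also meant to help power a later trial. The question is therefore how much the planned test loses, and whether that justifies a change.

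**Working it through.** **Inputs from the Data Analysis section.** 32 control patients and 64 per intervention arm. Return rates of 20% (control), 40% (audio) and 50% (video). One-sided alpha 0.1, so the critical value is z = 1.2816.

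**Inputs assumed, because the documents do not give them.** Half of each arm are women (control 16/16, intervention 32/32). Control return by gender is 20% plus or minus half the gap, with gaps of 0, 10, 20 and 30 points. The intervention adds 20 points (audio) or 30 points (video) in each gender.

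**Step 1: reproduce the stated power.** With d the difference in rates and p̄ the pooled rate,

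power = Φ[(d − 1.2816 × s0) / s1], where s0 = √[p̄(1 − p̄)(1/32 + 1/64)] and s1 = √[p1(1 − p1)/32 + p2(1 − p2)/64].

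- Video: p̄ = (6.4 + 32)/96 = 0.400, s0 = 0.1061, s1 = 0.0944. Power = Φ(1.739) = 95.9%; stated 96%.
- Audio: p̄ = (6.4 + 25.6)/96 = 0.333, s0 = 0.1021, s1 = 0.0935. Power = Φ(0.740) = 77.0%; stated 77%.

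The stated power therefore belongs to the unstratified test without continuity correction. With a correction the same formula gives 93.2% and 68.8%.

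**Step 2: why the level falls.** Under the null at 20%, the unstratified test uses a variance per patient of 0.20 × 0.80 = 0.16. With the arms balanced by gender and a gap g, the true variance is 0.16 − g²/4. The real level is about 1 − Φ[1.2816 / √((0.16 − g²/4)/0.16)].

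- g = 0.1: √(0.1575/0.16) = 0.992, 1 − Φ(1.292) = 9.8%
- g = 0.2: √(0.1500/0.16) = 0.968, 1 − Φ(1.324) = 9.3%
- g = 0.3: √(0.1375/0.16) = 0.927, 1 − Φ(1.382) = 8.3%

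**Step 3: exact enumeration.** All possible outcomes were enumerated for the planned pooled z test and for a gender-stratified CMH test without continuity correction. The table gives probabilities of rejection.

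| Assumed gap (control rates) | Level, planned | Level, CMH | Audio power, planned | Audio power, CMH | Video power, planned | Video power, CMH |
|---|---|---|---|---|---|---|
| 0 (20% / 20%) | .0980 | .0984 | .7757 | .7760 | .9590 | .9590 |
| 10 (15% / 25%) | .0961 | .0983 | .7770 | .7786 | .9600 | .9601 |
| 20 (10% / 30%) | .0905 | .0990 | .7811 | .7890 | .9632 | .9640 |
| 30 (5% / 35%) | .0811 | .0989 | .7885 | .8115 | .9686 | .9722 |

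The gain in power is 0.0, 0.2, 0.8 and 2.3 points for audio, and 0.0, 0.0, 0.1 and 0.4 points for video.

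**Step 4: sensitivity to the assumptions.** With a 19:13 gender split in control (38:26 in the intervention arm), audio power is .7757/.7770/.7809/.7878 planned and .7758/.7780/.7871/.8087 with CMH, which is almost the same. A separate simulation that set the gap as a gender odds ratio agrees. At an odds ratio of 3, audio power is 78.2% planned and 79.2% with CMH; at 5 it is 78.6% and 81.1%.

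**Step 5: the continuity correction.** A continuity-corrected CMH test in the balanced setting of Step 3 has an audio power of only 69.3% at a gap of 0 and 71.2% at a gap of 20 points. That loss exceeds anything gained from stratifying, so the amended text must rule the correction out.

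**The case against.** The strongest reply is that this is reviewer preference. The planned test is valid, type I error is not inflated in any scenario examined, and the stated power reproduces for exactly this test. The gain depends on a gender gap that the documents never give. At gaps up to 20 points it is less than 1 point of power, and no plausible conclusion of the pilot would change. The 95% interval is not a strong argument either. The stratified audio interval is 0 to 6% narrower over the four gaps, but its coverage is 94.1 to 94.2%, against 94.1 to 95.6% unadjusted. All of that stands, and it is why the point is minor.

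A second reply is that the protocol disclaims gender analyses. It does not disclaim this one. That remark concerns comparing effects between men and women. A CMH test remains one test per intervention and needs no power for gender effects.

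A third reply is that the conservatism depends on the arms being balanced within gender, and the Randomization section names a random number generator but no blocks. The numbers do rest on balance. However, the text says allocation is stratified by gender, in each arm and with fixed arm totals, so balance is the natural reading.

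Two stronger readings are tempting and should be resisted.

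- A reader might infer that ignoring the stratum makes the primary test wrong or the power figures unreliable. Steps 1 and 3 show neither.
- A reader might infer from the group-data sentence that FIT return cannot be split by gender for patients without a release form. The documents do not settle this. Table 1 describes the form as "Release of CRC screening results", which may concern results only. The mailed reminder "will be sent to participants who have not completed the FIT", so completion is tracked patient by patient at least at the health center. The data-exchange appendix is not among the documents reviewed.

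**Conclusion.** The mismatch between a gender-stratified design and an unstratified primary test is real, and its effect is small. With equal numbers of men and women balanced within arms, the planned test's one-sided level lies between 9.8% (no gap) and 8.1% (a 30-point gap), while CMH stays at 9.8 to 9.9%. Over the same range CMH adds 0.0 to 2.3 points of power for audio and 0.0 to 0.4 for video. The upper end needs control return rates of 5% and 35% by gender, which is extreme. Up to a 20-point gap the audio gain is at most 0.8 points.

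These figures rest on an assumed gap, an assumed gender split and balance within gender. The sample size, the stated power and the validity of the planned test are not in question. This is a minor improvement that aligns the analysis with the design.

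**What to change.** In the Data Analysis section, by a dated amendment made before outcomes by arm are examined, replace the sentence on the two comparisons with:

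*Each intervention will be compared with usual care by a Cochran-Mantel-Haenszel test stratified by gender (intent-to-treat, one-sided alpha 0.1, no continuity correction), with the Mantel-Haenszel risk difference and its 95% CI.*

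The Survey Non-Responders section shows that the study is under way and that patients are sorted by arm and FIT completion for follow-up. It does not say whether totals by arm have been looked at. If they have, keep the planned test as primary and report the stratified test as a sensitivity analysis.

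In FIT Results and Follow-Up, state whether the group data cover FIT return or only FIT results. Only if FIT return for patients without a release form arrives solely as group data, ask the health center for returned and not-returned counts by arm and gender (3 × 2 = 6 rows), subject to its disclosure check. The check matters because the cells are small: at 70% MRR return, 0.30 × 32 = 9.6 control patients have no form, or about 5 per gender if half are women.

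The cost is a mid-study wording change, one clarification and possibly one small table. No extra patients are needed. With the arms balanced by gender, CMH loses no power at any gap examined.

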### **Survey Non-Responders.**

Due to the low return of completed surveys, an additional follow-up will be conducted. A letter from the health center participating in this study will be sent to patients who have not returned a completed survey and: a) who have not completed the FIT test (Appendix AA), or b) who have completed the FIT test. If a patient calls the toll-free number and is willing to complete the telephone interview, a script (Appendix CC) will be read prior to starting the interview that will include obtaining verbal consent for the telephone interview.

After verbal consent has been received, the interview will start. A few introductory questions and the interview guides (Appendix DD) are the approved surveys with a few less questions to decrease burden. The six different interview guides are based on what arm of the study (usual care, audio brochure, video brochure) the person was sent and whether they completed or did not complete the FIT test. Participants will be mailed the \$25 gift card if they complete the telephone interview. This additional opportunity to collect information from patients is important for revising the intervention prior to testing in a future trial.

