### **Study Primary Outcome: FIT Return.**

FIT return at 2 months will be the primary outcome of this pilot study.

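### Could the added letter to survey non-responders act as a FIT reminder in the usual care arm, which has no planned reminder?

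*Combined protocol and SAP*

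**What the plan says.** The Study Primary Outcome section of the combined protocol and SAP fixes the endpoint: "FIT return at 2 months will be the primary outcome of this pilot study". The reminder paragraph under Intervention Groups gives the same two-month point.

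The planned reminder is part of the intervention package. Table 1 lists it for the audio and video arms only, and the Usual Care Group section lists none. It "will be sent to participants who have not completed the FIT about two weeks after the initial FIT test mailing based on community input".

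The Survey Non-Responders section then adds a contact, with this trigger: "Due to the low return of completed surveys, an additional follow-up will be conducted". The recipients are defined by a missing survey ("A letter from the health center participating in this study will be sent to patients who have not returned a completed survey") and are split into those "who have not completed the FIT test (Appendix AA), or b) who have completed the FIT test". Usual care is included: "The six different interview guides are based on what arm of the study (usual care, audio brochure, video brochure) the person was sent", and also on whether the FIT was completed. A patient who calls the toll-free number and consents is interviewed by telephone and receives the same $25 that every arm was already offered for the survey. The stated aim is to gather information for revising the intervention before a future trial. The section says nothing about when the letter goes out relative to month 2.

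**The concern.** The reminder is one of the components that separate the intervention arms from usual care. A second mailing from the health center, selected partly on an uncompleted FIT and sent to all arms, could work as a reminder whatever its purpose. For usual care patients it would be the first.

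Nothing in the section makes the letter wait for the 2-month window to close. A FIT prompted inside the window would count as a primary outcome event. Usual care has the highest assumed non-completion rate (80%, against 60% for audio and 50% for video). Even an equal prompting effect would therefore raise its return rate most, pull both comparisons toward no difference, and overstate the control rate used to plan the larger trial.

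**Working it through.** **1. Reproduce the planned power.** Inputs from Data Analysis: 32 control, 64 audio and 64 video patients; return rates 20%, 40% and 50%; one-sided alpha 0.10 (z = 1.2816). The formula is that of the two-sample test of proportions with pooled variance under the null:

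power = Φ[(d − z·SE0)/SE1], with SE0 = √{p̄(1−p̄)(1/32+1/64)} and SE1 = √{pC(1−pC)/32 + pT(1−pT)/64}.

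- Audio: p̄ = (6.4+25.6)/96 = 0.3333, SE0 = 0.1021, SE1 = 0.0935. Φ[(0.20 − 1.2816×0.1021)/0.0935] = Φ(0.740) = 77.0%. The plan states 77%.
- Video: p̄ = (6.4+32)/96 = 0.40, SE0 = 0.1061, SE1 = 0.0944. Φ[(0.30 − 1.2816×0.1061)/0.0944] = Φ(1.739) = 95.9%. The plan states 96%.

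**2. If the letter follows month 2.** A FIT it prompts falls outside the endpoint. Both differences and both power figures are unchanged.

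**3. If the letter arrives inside the window.** Let r be the share of all non-completers who are prompted to return in time. The documents give no value, so every r below is an assumption. Return rates become 0.20+0.80r (control), 0.40+0.60r (audio) and 0.50+0.50r (video). With equal r in all arms the differences are 0.20(1−r) and 0.30(1−r), so each shrinks only by the fraction r.

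| r control | r audio/video | Difference, audio / video (points) | Power, audio / video |
|---|---|---|---|
| 0 | 0 | 20 / 30 | 77.0% / 95.9% |
| 2.5% | 2.5% | 19.5 / 29.25 | 74.4% / 94.7% |
| 5% | 5% | 19 / 28.5 | 71.8% / 93.4% |
| 10% | 10% | 18 / 27 | 66.9% / 90.4% |
| 10% | 5% | 15 / 24.5 | 56.1% / 85.6% |

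**4. What r means here.** The letter goes only to non-completers who also returned no survey, and only those still inside the window can matter. If s is the share of non-completers meeting both conditions and u is the effect among them, then r = s×u. With s = 50% and u = 5%, both assumed, r = 2.5%, the second row. The last row needs 10% of all usual care non-completers to respond and half that rate in the other arms. Nothing in the documents supports either rate or the gap between them.

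**5. Scale.** Expected usual care non-completers number 0.80×32 = 25.6, so r = 5% means 25.6×0.05 = 1.3 extra returns. The 95% confidence interval for the audio–control difference has a half-width of 1.96×0.0935 = 0.183, about 18 points, against a shift of 1 point.

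**6. What the text suggests about timing.** The trigger is a survey return already seen to be low, against the 85% expected. Letters and interview guides are sorted by whether the FIT was completed. The purpose looks ahead to the next trial. Each fits follow-up after outcome collection; none proves it.

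**The case for a change.** The strongest case is that silence permits the harm. A low survey return may be noticed before every patient's window has closed. The Randomization section continues until 160 patients are randomized and does not say that all kits are mailed together, so staggered mailing could leave later patients exposed.

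The outcome sentence in the Usual Care Group section also omits the two months, and no section says when the two months start. Late correction could be awkward: for patients without a signed medical record release, the study team receives only grouped data by arm, and survey non-responders may often be in that group.

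Part of this stands. The timing is not stated, and contamination cannot be excluded from the text alone. The rest carries less weight. The section devoted to the primary outcome fixes month 2 for the whole study, so the shorter usual care sentence does not create a second endpoint. Kit mailing is the natural start, since the reminder is timed from it. FIT results go from the laboratory to the health center, so the center is placed to apply the cut-off before it supplies counts by arm. Finally, the letter is described as a route to a survey interview; Appendix AA, which might show that it also urges FIT completion, is not available.

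**Conclusion.** The concern does not call for a change. The plan states no rule that yields a wrong result: it fixes the endpoint at 2 months and leaves unwritten the date of a survey follow-up whose description fits a later point. Holding the letter until the window closes is what a sensible study team would do anyway, and writing it down would leave the planned analysis and its power as they are.

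If letters did go out early, the expected bias is toward no difference. It would be 1 to 1.5 points if 5% of all non-completers in each arm responded, and smaller once only in-window patients without a survey are counted. It could reach 5 to 5.5 points (20 to 15 and 30 to 24.5) only under an unsupported differential response. All of these rest on assumed rates, on the planned return rates of 20%, 40% and 50%, and on the letter prompting FIT completion at all. For a pilot that describes its test as preliminary, this remains a minor gap in the description.
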